7.1 Primary Objective

The primary objective of this study is:

- To demonstrate a significant improvement of PPPASI at week 20 compared with baseline in moderate to severe chronic palmoplantar pustulosis under apremilast therapy.

7.2 Secondary Objective(s)

The secondary objectives of the study are:

- To evaluate an improvement of PPPASI at all assessment times compared with baseline in moderate to severe chronic palmoplantar pustulosis under apremilast therapy.
- To evaluate differences during the treatment with apremilast in life quality assessment measures: Dermatology Life Quality Index (DLQI) at all assessment times compared with baseline
- To evaluate safety of apremilast in patients with moderate to severe palmoplantar pustulosis

Exploratory objectives are:

- Time course of Hand and Feet Physician Global Assessment (H&F PGA) at all assessment times.
- Pustules count 50 response and Pustules count 75 response, defined as a 50% and 75% decrease in Pustules count from baseline, during the 20 weeks treatment period
- To evaluate differences in the mean change from baseline at all assessment times of VAS pruritus / itch, VAS discomfort / pain at all assessment times relatively to day 0 (baseline)
- To evaluate changes in Psoriasis Area Severity Index (PASI), Physician Global Assessment (PGA) and dynamic H&F PGA if plaque psoriasis is present between baseline and all assessment times
- To explore the effect of apremilast on immunological markers in serum / plasma
- To explore the effect of apremilast on immunological markers in skin biopsies (sub-study, see Section 12.1.10.2)

8 Study Design

This study will be conducted in accordance with applicable laws and regulations including, but not limited to, the ICH E6 guideline 'Note for Good Clinical Practice' (CPMP/ICH/135/95) (2) based on the principles of the Declaration of Helsinki (3). The study will be duly conducted in compliance with the Medicinal Products Act (Arzneimittelgesetz AMG), (§§ 40-42) (1). An independent ethics committee and the competent authority must review and approve the study before any patients are enrolled.

8.1 Description of the Study Design

This is a multicenter, open-label, single-arm, phase II, pilot study to evaluate the efficacy and safety of apremilast involving approximately 20 patients with PPP. The screening period is up to 4 weeks and treatment takes place over 20 weeks per patient. No follow up period takes place. No extension is planned.

Recruitment period is 4 months; hence study duration from FPI to LPO is approx. 9 months. 4 patients per site are expected to be recruited, assuming enrolment of both genders with distribution according to prevalence of condition. If recruitment is not running as anticipated after 2 months, recruitment will be opened to become competitive.

Patient recruitment will take place at approximately 5 sites in Germany. The investigators should have relevant expertise in diagnosing and treating PPP or be specialized in dermatology. Patients will be enrolled until 20 patients are included into the study. Drop-outs will not be replaced.

Please refer to the Study Flow Chart in the synopsis for the time schedule of the assessments.

Five visits per patients are planned including:

Visit 1 at week -4 - -1 (screening)

Visit 2 at week 0 (baseline)

Visit 3 at week 4

Visit 4 at week 12

Visit 5 at week 20 (end of study)

After completion of participation in the study, patients are advised to follow medical management of their treating physician (see as well Section 10.6.1).

8.2 Study Endpoints

8.2.1 Primary Endpoint(s)

- Percentage change from baseline in PPPASI after 20 weeks of treatment with apremilast

8.2.2 Secondary Endpoint(s)

- Absolute and percent change from baseline in PPPASI during the 20 weeks treatment period

- PPPASI 50 response and PPPASI 75 response, defined as a 50% and 75% decrease in PPPASI from baseline, during the 20 weeks treatment period
- DLQI bands (0-1 no effect, 2-5 small effect, 6-10 moderate effect, 11-20 very large effect, 21-30 extremely large effect) during the 20 weeks treatment period
- Absolute and percent change from baseline in DLQI during the 20 weeks treatment period
- Safety as assessed by treatment-emergent adverse events (TEAEs), vital signs and physical examination

8.2.3 Exploratory Endpoints

- Absolute and percentage change from baseline in level of immunological markers in plasma / serum during the 20 weeks treatment period with apremilast
- Percentage change from baseline in level of immunological markers in skin biopsy samples after 20 weeks of treatment with apremilast (sub-study)

8.3 Patient Identification

Patients will be identified from the investigator's database.

Upon enrolment, each patient will receive a 5 digit patient number (XX-XXX) starting with:

- 2 digits for the site
- separated by hyphen
- 3 digits for the patient (ascending order)
- E.g. 01-001

Within each site, the investigator will allocate the patient numbers in ascending order of patients screened and include each screened patient in a screening, enrolment and randomization log with site number, a running patient number and year of birth. All patients will be identified by the unique patient number in a patient identification log in the investigator site file.

As this study is an open label, single-arm study no randomization will take place.

Patients who drop out will not be replaced.

8.4 Withdrawal of Patients

In accordance with the informed consent and the Declaration of Helsinki (3), any patient can refuse to participate or withdraw from the study without giving reasons at any time without any penalty or loss of benefits to which the patient is otherwise entitled. When appropriate, patients may be placed on other conventional therapy when clinically indicated.

Patients have to be withdrawn from the study by the investigator if at least one of the following events occurs

- Withdrawal of informed consent
- Pregnancy

- Any study medication discontinuation or dose reduction during the up-titration (days 1 to 6)
- Study medication discontinuation (i.e. no study medication taken) during the maintenance phase irrespective of the reason for more than 5 days in a row or a total of 10 days, or dose reduction (i.e. ≤1 tablet per day) during the maintenance phase (from day 6 onwards) irrespective of the reason for more than 5 days in a row or a total of 10 days
- Major protocol violation (e.g. patient requires the use of medication and / or treatments not permitted by the study protocol)
- Severe treatment emergent adverse events that in the opinion of the investigator results in a risk / benefit assessment with negative results
- Patients are also to be withdrawn at any time if the investigator concludes that it would be in the patient's best interest for any reason
- Depression worsening under treatment

Patients are to be considered withdrawn if they state an intention to withdraw, fail to return for visits, become lost to follow up for any other reason, or if any of the following occur: discovery of patient ineligibility; errors in treatment compliance; missed or incorrect assessments.

Protocol violations do not necessarily lead to the patient's withdrawal unless they constituted a significant risk to the patient's safety. For patients not completing the entire study, all used and unused study drug should be returned by the patients to the defined personnel at the site.

Patients who prematurely withdraw from the study will be scheduled for an end-of-study visit as soon as possible (11.2.6). An end-of-study page will be completed, giving the date and primary reason for stopping treatment if provided. Patients prematurely withdrawn from the study will not be replaced. Patients who prematurely withdraw from the study for any reason at any time are excluded from the continuation of the study and will be treated if indicated as for any event still ongoing at the end of a clinical study according to standard practice under supervision by an experienced dermatologist or will be referred to a dermatologic practice for further treatment according to standard practice. In the case of premature discontinuation due to an adverse event (AE), the investigator should ensure that the patient receives a suitable therapy appropriate to his / her conditions.

For patients who are lost to follow-up (i.e., those patients whose status is unclear because they fail to appear for study visits without stating an intention to withdraw), the investigator should show due diligence by documenting in the source documents steps taken to contact the patient, e.g., dates of telephone calls, registered letters, etc.

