10.7 Permitted Study Medication Dose Adjustments and Interruptions

For patients who are unable to tolerate the protocol-specified dosing scheme, the following interruptions and / or dose adjustments are permitted:

At the discretion of the investigator treatment may be interrupted during the maintenance phase for a maximum of 5 days in a row or a total of 10 days (see also Section 8.4). In addition, a reduction of the dose from day 6 onwards (only during the maintenance phase) is allowed: the dose may be reduced to one tablet (30 mg) per day for a maximum of 5 days in a row or a total of 10 days. All interruptions and adjustments of study treatment must be recorded in the Case Report Form (CRF).

Patients who experience any uncomfortable event should contact the investigator to assess the need for safety assessments (AEs and SAEs). In case of any AE a discontinuation may be decided by the principal investigator.

AEs and SAEs will be recorded in the corresponding AE page of the CRF. In case of a SAE, a SAE form is to be completed (see also Section 13.3). If the patient does not prematurely discontinue the study, the next regular scheduled visit should be performed as planned. If the patient does prematurely discontinue the study at a visit on site, this visit should be considered as the end-of-study visit.

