11.2.6 Early Termination Visit

In case of early termination of a patient, effort will be made to schedule an early termination visit and assess the following, if possible:

- The reason for discontinuation will be documented.
- A urine pregnancy test (β -hCG) will be performed in females with childbearing potential.
- Physical examination including weight and vital signs will be assessed.
- PsA and comorbidity will be documented.
- Concomitant medication will be documented.

- The patient will be interviewed concerning the occurrence of AEs.
- Serum and plasma samples will be taken.
- Biopsies will be taken (two lesional biopsies from feet or hands). The taking of biopsies is optional.
- The investigator will
 - ask the patient to rate their pruritus and pain on hands and feet using the VAS.
 - assess the PASI, PPPASI, PGA, H&F PGA, dynamic H&F PGA and pustules count.
- Study medication will be collected for drug accountability and documentation for treatment compliance.

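### Protocol 8.4 counts any compliance error or missed assessment as withdrawal, without a threshold, contradicting its own limits; applied literally, it would cost week-20 PPPASI values for no safety reason

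*Protocol*

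**What the plan says.** Protocol 8.4 lists events for which the investigator must withdraw a patient. Two concern dosing:

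- "Any study medication discontinuation or dose reduction during the up-titration (days 1 to 6").
- Taking no drug, or at most one tablet a day, "during the maintenance phase irrespective of the reason for more than 5 days in a row or a total of 10 days".

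The list also includes a major protocol violation, severe adverse events, worsening depression and the patient's best interest.

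A separate sentence then says that patients count as withdrawn if they state an intention to withdraw, do not come back for visits, are lost to follow-up, or "if any of the following occur: discovery of patient ineligibility; errors in treatment compliance; missed or incorrect assessments". The next paragraph says: "Protocol violations do not necessarily lead to the patient's withdrawal unless they constituted a significant risk to the patient's safety".

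The consequence of withdrawal is also in 8.4: "Patients who prematurely withdraw from the study for any reason at any time are excluded from the continuation of the study". Withdrawn patients are not replaced. Under 11.2.6, "effort will be made to schedule an early termination visit and assess the following, if possible"; PPPASI is among those assessments.

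Protocol 10.7 allows for intolerance: at the investigator's discretion "treatment may be interrupted during the maintenance phase for a maximum of 5 days in a row or a total of 10 days", and in addition "the dose may be reduced to one tablet (30 mg) per day for a maximum of 5 days in a row" or 10 days in total. Protocol 10.9 has dosing irregularities, including missed doses and overdoses, recorded in the CRF. Protocol 14.1 grades deviations as minor or major at the data review meeting.

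**The concern.** The sentence gives no number, no grade of severity and no room for investigator judgement for compliance errors or missed assessments. Read as written, one forgotten maintenance tablet or one unfilled VAS makes the patient a withdrawal, although the bullets above it tolerate days without drug and set no withdrawal for a missed item.

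The primary endpoint is the percentage change in PPPASI at week 20, in 20 patients. A withdrawal decided at visit 3 or 4 removes the observed week-20 value. The patient also leaves the per-protocol set, which requires study completion (Protocol 14.2, SAP 5). The primary FAS analysis then carries forward a value from week 4, week 12 or an early termination visit (SAP 6.3.5, 6.6). The observed-case FAS table (14.2.1.1) and the per-protocol table (14.2.1.3) lose the patient altogether. Sites that read the text differently would also withdraw patients by different rules.

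**Working it through.** **1. The texts side by side.** The plan gives no figure that depends on this rule, and the sample size has no statistical basis (Protocol 14.11), so there is nothing to reproduce.

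| Text | A few scattered missed maintenance tablets | One missed assessment |
|---|---|---|
| 8.4, deemed-withdrawal sentence | withdrawn | withdrawn |
| 8.4, maintenance limits | stays | not addressed |
| 8.4, next paragraph | stays, absent a significant safety risk | stays, absent a significant safety risk |
| 8.4, major-violation bullet | implies minor violations stay | implies minor violations stay |
| 10.7 | stays, if an interruption or reduction allowed for intolerance | not addressed |
| 10.9 | documented | not addressed |
| 14.1 | graded minor or major | graded minor or major |

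Rows 2 and 3 contradict row 1. The maintenance limits apply whatever the reason, so they cover patient error, and the two rules give different answers for the same event. The remaining rows are in tension with row 1 without contradicting it.

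**2. What the documents size.** Tablets scheduled to day 140: 1 + 2 × 139 = 279. Ten days without drug is 20 tablets, 20/279 = 7.2%. If 8.4 withdraws at the tenth day, nine days are tolerated: 18/279 = 6.5%. If the one-tablet days of 10.7 come on top, tolerance is 30/279 = 10.8%. The deemed-withdrawal sentence tolerates none.

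**3. When an error costs the week-20 value.** Compliance is checked and medication returned at visits 3, 4 and 5. Only errors found by visit 4 (day 84) can remove visit 5. Tablets to day 84: 1 + 2 × 83 = 167.

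**4. Illustration, on assumptions not in the documents.** Let each tablet be missed with probability p, with intra-patient correlation ρ. The literal rule reaches P(at least one miss in 167): 1 − (1 − p)^167 if independent, otherwise beta-binomial with a = kp, b = k(1 − p), k = (1 − ρ)/ρ. The comparator is 8.4's explicit rules, by simulation: any miss on days 1 to 6, or later more than 5 days in a row or more than 10 in total with a tablet missed. Cells show literal rule / explicit rules, then extra patients of 20.

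| ρ | p = 0.5% | p = 1% | p = 2% |
|---|---|---|---|
| 0 | 56.7 / 5.4%; 10.3 | 81.3 / 10.4%; 14.2 | 96.6 / 20.0%; 15.3 |
| 0.05 | 19.7 / 4.9%; 3.0 | 35.5 / 9.6%; 5.2 | 58.5 / 19.1%; 7.9 |
| 0.1 | 12.7 / 4.3%; 1.7 | 23.9 / 8.4%; 3.1 | 42.1 / 16.5%; 5.1 |
| 0.2 | 7.5 / 3.2%; 0.9 | 14.4 / 6.4%; 1.6 | 26.8 / 12.4%; 2.9 |

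Extra patients = 20 × (literal − explicit). The comparator counts one forgotten tablet in titration as a discontinuation or reduction, which 8.4 does not say outright. With independent misses this supplies essentially all of it: 1 − 0.995^11 = 5.4%.

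**5. Assessments, same caveat.** Visit 3 has 7 efficacy items and visit 4 has those plus DLQI, 15 in all. If each is missed or wrong independently with probability 0.5%, 1% or 2%, then 1 − (1 − p)^15 = 7.2%, 14.0% or 26.1% of patients have at least one; at ρ = 0.1, 4.5%, 8.8% or 16.8%.

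**The case against.** The strongest reply is that the documents themselves point away from literal use. The paragraph after the sentence says violations need not lead to withdrawal, and the mandatory list names only major violations. Section 10.9 records missed doses as a routine matter, and the SAP counts missing values and leaves secondary ones unreplaced, which presumes that patients with gaps continue. This stands as evidence of intent. It does not remove the conflict, because the sentence is unconditional and names the events.

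Three stronger readings are tempting and not supported:

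- A reader might infer that any tablet missed before visit 5 costs the week-20 PPPASI. An error after visit 4 would normally surface at visit 5, when PPPASI is taken anyway.
- A reader might infer that 10.7 flatly contradicts the sentence. Section 10.7 covers interruptions allowed by the investigator for intolerance, and these are arguably not errors.
- A reader might infer from the independent-miss row that most patients would be lost. That row rests on assumed rates and on misses that do not cluster within patients.

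The loss is also softened. Patients stay in the FAS, a withdrawal decided at a site visit makes that visit the end-of-study visit (10.7), and the per-protocol analysis is only supportive.

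**Conclusion.** The contradiction within 8.4 holds on the text alone. The SAP does not resolve it. Whether it does harm depends on how sites read the sentence, which the documents do not show. Under literal use, the loss falls on patients whose error is found at or before visit 4: no observed week-20 PPPASI, no per-protocol membership, and an earlier carried-forward value in the primary analysis. Errors found only at visit 5 cost no week-20 PPPASI.

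The number affected cannot be derived from the documents. The illustration spans about 1 to 15 extra patients of 20, too wide to size the problem; it shows only that the outcome turns on unstated miss rates and clustering. The point is worth acting on because the trial has 20 patients without replacement, these withdrawals would have no safety reason, and the correction is cheap.

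**What to change.** In Protocol 8.4:

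1. Delete the last two items of the deemed-withdrawal list (compliance errors; missed or incorrect assessments). Keep discovery of ineligibility.
2. Change the missed-visit trigger to *permanently fail to return for visits*, so that one missed visit does not meet two opposing rules.
3. Add: *Compliance errors (including overdoses) that do not meet a withdrawal criterion listed above, and missed or incorrect assessments or a single missed visit, are recorded as protocol deviations (14.1), and the patient stays on the visit schedule through the week-20 PPPASI unless there is a significant safety risk.* Overdoses need naming because the existing limits cover only stopping and reduction.
4. Word both maintenance limits as *more than 5 days in a row or more than 10 days in total*. At present exactly 10 days is allowed by 10.7 but can be read as a withdrawal in 8.4.

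Leave the days 1 to 6 rule and the safety withdrawals unchanged. No visits or patients are added. The cost is a few more deviations to classify at the data review meeting already planned.

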8.5 Discontinuation of Entire Study

The study must be terminated prematurely for the following reason(s):

- Updated risk / benefit assessment with negative results (sponsors' and coordinating investigators' assessment)
- Study cannot be completed within a reasonable time frame due to slow patient recruitment

The regulatory authorities and the Institutional Review Board (IRB) / Independent Ethics Committee (IEC) must be notified of premature termination of the study. The investigator may

be informed of additional procedures to be followed in order to assure that adequate consideration is given to the protection of the patient's interests.

In addition, a site may be discontinued at any time by the sponsor and all study materials removed. Possible reasons for termination of the study at the site include, but are not limited to:

- Safety concerns based on reported data
- Unsatisfactory enrolment with respect to quantity or quality
- Inaccurate or incomplete data collection
- Falsification of records
- Failure to adhere to the protocol

9 Selection of Patients

9.1 Inclusion / Exclusion Criteria

The investigator must ensure that all patients who meet the following inclusion and exclusion criteria are offered enrolment in the study. Patients will be enrolled if all inclusion and none of the exclusion criteria are met. All patients screened to participate in the study will be documented and the reason for study exclusion will be documented to avoid enrolment bias.

9.1.1 Inclusion Criteria

- Male and female patients aged 18 years or more at screening visit.
- Patients with chronic PPP (disease history of at least 6 months of diagnosis), who are eligible for treatment with systemic therapy defined as having PPP inadequately controlled by topical treatment and / or phototherapy and / or previous systemic therapy
- Patients with chronic moderate to severe PPP defined as patients with a PPPASI ≥ 12 with or without concomitant plaque-type psoriasis
- Negative result of a urine pregnancy test taken at screening and at baseline for all women, except those who are surgically sterile or at least 1 year postmenopausal (i.e. at least 12 consecutive months with amenorrhea without other known or suspected medical cause)
- Willingness and capability of using a highly effective contraceptive measures from Screening visit until the end of at least one menstrual cycle (but not less than 28 days) following discontinuation of apremilast as defined below:
 - Female patient of childbearing potential (fertile, following menarche and until becoming post-menopausal unless permanently sterile) using a highly effective method of contraception OR female patients of non-childbearing potential (surgically sterilized [e.g. hysterectomy, bilateral salpingectomy and bilateral oophorectomy] or post-menopausal)
 - Male patient, and their female partner of childbearing potential, using a highly effective method of contraception
 - Adequate contraceptive method defined as:
 - A method with less than 1% failure rate (e.g. permanent sterilization, hormone implants, hormone injections, some intrauterine devices, or vasectomized partner)
- OR
 - The use of two methods of contraception (e.g. one barrier method [condom, diaphragm or cervical/vault caps] with spermicide and one hormonal contraceptive [e.g. combined oral contraceptives, patch, vaginal ring, injectables and implants])
- Patient is capable of understanding and giving written, voluntary informed consent before study screening.
- Willingness and capability of complying with all study procedure requirements, as per the Investigator's judgment (e.g. patient able to swallow the apremilast tablets, blood sampling).

